The primary objective of the study is to evaluate the feasibility and efficacy of the new medical device in treatment of paediatric patients with forearm fractures. The key variables in this assessment are the evaluation of the functional and clinical outcome by measuring range of motion in forearm, wrist and elbow (e.g. measuring supination/pronation and flexion-extension movements), and subjective pain assessment during recovery. The primary objective will be met if these outcomes in the treatment group are at least comparable to those of the patients treated with standard of care (TEN nail), interpreted by using the Price's classification system (<15 degrees of change in motion range is excellent clinical outcomes), and Flynn's criteria for upper extremity assessment (<10 degrees of change in motion range justifies satisfactory outcomes). The potential difference less than 10 degrees are to be determined not clinically significant. The raw results of clinical measurements and statistical significance of each finding are to be reported.

Secondary Objectives

The secondary objectives of the study are to evaluate the radiographic outcome of the forearm fracture treatment in patients treated using the study device. The key variables in assessment of these objectives are:

- fracture reduction and angulation,
- formation of bridging callus and consolidation (union, delayed union, non-union and malunion)

The method in assessment of key variables is plain radiographic evaluation. The secondary objective will be met if these outcomes in the treatment group are at least comparable to those of the patients treated with standard of care (TEN nail). According to the previous literature, angular deformity of <10 degrees in radius and/or ulna is to be determined not clinically significant [27-29].

Soft-tissue reaction against the biodegradable implant are to be studied by Magnetic Resonance Imaging (MRI) for a randomly selected sub-group of at least 10 patients.

Design of the Clinical Investigation

Type and Design of The Study

This is a randomized parallel-group **two-centre** study on the use of bioabsorbable intramedullary nail device for fixation of the radial and ulnar shaft fractures in children. All patients will receive the standard of care for other injuries caused by the trauma.

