1.1.11 Primary Performance Variable

Evaluation of functional and clinical outcome consists of following determinations:

Clinical Investigation Plan

Bioabsorbable Intramedullary Nail Fixation of Forearm Fractures in Children

- Measurements of the range of motion (ROM) in the forearm, expressed as degrees \pm SD
 - Loss of supination and pronation of the forearm (graded according to the table below),
 - Loss of flexion and extension of elbow and
 - Loss of dorsiflexion and palmar flexion of the wrist, graded according to the Flynn's criteria (<10 degrees of change are excellent or good i.e. satisfactory; >10 degrees of change are fair or poor i.e. unsatisfactory); and Price's classification.
- General pain and pain at fracture site assessed by VAS, expressed as mm \pm SD
 - Duration of post-operative medication for pain

Table 1 Classification of outcome, graded using a system described by Price [25]

Outcome	Loss of Forearm Rotation and Symptoms
Excellent	$\leq 15^\circ$ loss of forearm rotation and no complaints with strenuous activity
Good	A loss of forearm rotation of 15° to 30° and only mild complaints with strenuous physical activity
Fair	A loss of forearm rotation of 30° to 90° and mild complaints during activities of daily living
Poor	All other outcomes

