1.1.14 Other Variables

Other variables documented in CRF are:

- Operation time
- Number of days lost from usual activities
 - Parents lost working days
- Length of hospitalization stay
- Complaints in daily living
- Esthetics

Statistics

Recommended statistical methods will be applied. All deviations made after approval of the CIP will be described and justified in the final study report.

Sample Size Considerations

Primary outcome variable in this study is loss of supination and pronation within 6, 12, 26, 52, and 104 weeks after surgery. The non-inferiority margin is set to be 80 % in the calculations (=Power).

It is previously known that the forearm pronation in this age group is 81.2 degrees (95% CI 79.6-82.28) and 79.6 degrees (95% CI 78.8-80.4) in girls and boys, respectively. The corresponding supination archs are 90.0 degrees (95% CI 88.0-92.0) and 87.8 degrees (95% CI 85.7-89.9). [26] The standard deviation (SD) is 6.1 degrees in pronation and 7.6 degrees in supination. We determined that the new method (ActivaNail –intramedullary fixation) should

Clinical Investigation Plan

Bioabsorbable Intramedullary Nail Fixation of Forearm Fractures in Children

result to the forearm rotational range of motion that is not more than 15 degrees lower, compared to the rotational range of motion in TEN group, according to the Price's classification (<15 degrees of decrease refers to excellent outcome).

Difference between means in the groups is set as 7.0 and the Alpha as 0.05. The sample size is estimated to be 13 experimental subjects and 13 controls according to an unpaired two sample Student t test. This study population will also be exclusively large enough to recognize decrease in the ROM that is clinically significant (>15 degrees of decrease in supination or pronation in ActivaNail compared to TEN group).

Statistical Hypothesis

The following hypothesis will be tested for the primary efficacy variable:

H₀: Investigational device is inferior to comparative devices

H₁: Investigational device is non-inferior to comparative devices

The non-inferiority limit is set to 80 %. Thus, non-inferiority is shown if the upper limit of the 95% confidence interval for the difference is less than or equal to 5 %.

Statistical Methods

All operated subjects who reach the 2-year follow-up will be included in the statistical analysis. Study data will be tabulated by treatment groups with descriptive summary statistics.

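### Sections 8.1 and 10.1 give two different limits, 10 and 15 degrees, for the tolerable difference from TEN, and the decision rule in 10.2 is not in degrees

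*Protocol*

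**What the plan says.** Section 8.1 (Primary Objectives) counts the primary objective as met if "these outcomes in the treatment group are at least comparable to those of the patients treated with standard of care (TEN nail"), read through the Price and Flynn systems. The next sentence is: "The potential difference less than 10 degrees are to be determined not clinically significant".

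Section 10.1 (Sample Size Considerations) asks that the new nail "result to the forearm rotational range of motion that is not more than 15 degrees lower" than in the TEN group, and cites Price's classification for the figure. It adds that the sample is large enough to detect a "decrease in the ROM that is clinically significant (>15 degrees of decrease in supination or pronation in ActivaNail compared to TEN group").

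The same section applies the word margin to something else: "The non-inferiority margin is set to be 80 % in the calculations (=Power"). Section 10.2 (Statistical Hypothesis) repeats 80 % as the limit and then states that "non-inferiority is shown if the upper limit of the 95% confidence interval for the difference is less than or equal to 5" %. Neither percentage has a stated base.

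Under Primary Performance Variable (1.1.11), Table 1 gives the Price grades as one child's loss of forearm rotation together with that child's symptoms. Flynn's criteria there read "<10 degrees of change are excellent or good i.e. satisfactory; >10 degrees of change are fair or poor i.e. unsatisfactory".

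**The concern.** In a non-inferiority trial the margin defines success. Here one comparison, new nail against TEN, carries two limits in degrees, and nothing in the protocol says which one decides. A result compatible with a deficit of 12 degrees satisfies 10.1 but lies outside the range that 8.1 sets aside as unimportant. With the choice left open, it could be made after the data are seen.

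The justification for 15 degrees is also weak. Price's cut-off grades a single child's own loss. A tolerance for a difference between group means is a different quantity and needs its own argument. Flynn's system, which the protocol also adopts, already calls a change above 10 degrees unsatisfactory.

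**Working it through.** **Inputs.** From 10.1: SD 6.1 (pronation) and 7.6 (supination), difference between means 7.0, alpha 0.05, power 80%, 13 per group. From the Statistical Methods section: two-sided tests and 95% confidence intervals. Limits: 10 degrees (8.1) and 15 degrees (10.1). A deficit is counted as positive when the new nail is worse.

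**1. The plan's own figure.** Two-sample t test, difference 7.0, SD 6.1, two-sided 5%, n = 13 per group: power 80.1%. The stated 13 is reproduced. With SD 7.6 the power is 61.5%, and 20 per group would be needed for 80%. Neither 10 nor 15 degrees enters this calculation, so the stated sample size does not show which limit was meant.

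**2. Width of the interval.** SE = SD × √(2/13); half-width = t(0.975, 24 df) × SE, with t = 2.064.
- SD 6.1: SE = 2.393, half-width 4.94.
- SD 7.6: SE = 2.981, half-width 6.15.

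**3. Largest observed deficit that passes** (limit minus half-width, with the SD at its planned value):

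| Limit | SD 6.1 | SD 7.6 |
|---|---|---|
| 15 degrees | 10.06 | 8.85 |
| 10 degrees | 5.06 | 3.85 |

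Observed deficits between the two rows pass under one limit and fail under the other.

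**4. How often the verdicts differ.** Let U be the upper 95% limit. P(U below margin M at true deficit d) is the probability that a non-central t with 24 df and non-centrality (M − d)/SE exceeds 2.064. The verdicts differ when U lies between 10 and 15, so the probability is P(pass at 15) − P(pass at 10).

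| True deficit | SD | Pass at 15 | Pass at 10 | Verdicts differ |
|---|---|---|---|---|
| 5 | 6.1 | 98.0% | 51.8% | 46% |
| 5 | 7.6 | 89.6% | 36.3% | 53% |
| 7 | 6.1 | 89.4% | 22.5% | 67% |
| 7 | 7.6 | 73.1% | 16.0% | 57% |
| 10 | 6.1 | 51.8% | 2.5% | 49% |
| 10 | 7.6 | 36.3% | 2.5% | 34% |

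**5. The other reading of 8.1.** Suppose the 10 degrees applies to the point estimate. A conflict then needs an estimate of 10 or more together with U no greater than 15. Simulation with 13 per group at true deficits of 5 and 7 puts this at about 0.1% to 2% of trials.

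**6. Power of a 10-degree margin, 13 per group** (one-sided 2.5%, same formula with M = 10):
- True difference 0: 98.0% (SD 6.1) and 89.6% (SD 7.6). At a 15-degree margin both exceed 99%.
- True deficit 7: 22% and 16%. For 80% power, 66 or 102 per group would be needed.

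**7. Total rotation instead of each movement.** The protocol gives no SD for the sum. With an assumed correlation r between pronation and supination, SD = √(6.1² + 7.6² + 2r × 6.1 × 7.6). This is 9.7 at r = 0 and 11.9 at r = 0.5. Power at a 10-degree margin with zero true difference is then about 71% and 54%.

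**The case against.** The strongest reply is that 8.1 states no confidence-limit rule. It says only that a difference below 10 degrees is not clinically significant; it does not say that 10 or more is worse. On a point-estimate reading, an estimate of 6 with an upper limit of 12 is acceptable under both sections, and step 5 shows that conflicts are then rare. This stands. The 46% to 67% figures depend on applying both limits to the upper confidence limit. That is the form of rule 10.2 uses, but it is not written in 8.1.

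The meaning of the 10 degrees can also be questioned. The sentence follows the Price and Flynn cut-offs and covers forearm, wrist and elbow together, while 1.1.11 ties forearm rotation to the Price table. So the documents do not establish that 10 is the intended limit for rotation. They still give two unreconciled figures for a comparison with TEN.

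It is also true that 15 degrees is never formally named the margin; that label goes to 80 %, and 10.2 decides on 5 %. This does not resolve the conflict, because neither percentage can be converted to degrees from the text.

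A reader might infer that the 15-degree limit lets the trial pass a device that takes half of the children out of Price's excellent grade. The documents do not support that. It requires a true mean deficit of 15 degrees with no loss under TEN, and at that deficit a 15-degree margin is passed only 2.5% of the time, the test's ordinary error rate. A reader might likewise infer that a result could routinely be non-inferior and clinically worse at once. Section 8.1 never calls 10 or more worse, and with 13 per group an observed deficit of 10 barely passes at 15 for SD 6.1 (maximum 10.06) and does not pass for SD 7.6.

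**Conclusion.** The inconsistency is in the text and should be corrected. Section 8.1 implies a 10-degree threshold against TEN, 10.1 a 15-degree one on a borrowed individual-level cut-off, and 10.2 a percentage rule that matches neither. With both limits on the upper 95% confidence limit, 13 per group and the plan's SDs, the choice changes the conclusion in roughly half to two thirds of trials at true deficits of 5 to 7 degrees; 7 is the plan's own design difference. With 8.1 on the point estimate, the practical conflict is small, but the protocol would still lack a single usable margin. These figures assume normal data, equal groups and the plan's SDs. The stated sample size of 13 is reproducible and is not affected by this point.

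**What to change.** Reconcile 8.1, 10.1 and 10.2 into one pre-specified between-group margin in degrees:
- State that non-inferiority is judged on the upper 95% confidence limit for the difference in mean loss of motion.
- Say whether the margin applies to pronation and supination separately or to total rotation; 10.1 uses both wordings.
- Replace the 80 % and 5 % wording in 10.2, and in 10.1 label 80 % as power only.
- Keep Price and Flynn as per-child grades, and remove Price as the justification for a group limit.

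The 10 degrees already in 8.1 is the natural conservative choice, though the documents do not dictate it. If it is adopted, state its power with the conditions. With 13 per group and truly equal devices it is 98% for pronation and 90% for supination. It is 22% or 16% if the true deficit is 7 degrees, and about 54% to 71% for total rotation at zero true difference (SD 11.9 to 9.7, assumed).

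The cost is protocol wording. No more patients are needed if the devices are truly equal and the margin applies to each movement separately. If a real deficit near 7 degrees is expected, or total rotation is chosen, 13 per group falls short of the plan's 80% at a 10-degree margin.

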The conventional level of 5% will be considered the level of statistical significance. All tests will be two-sided. Accordingly, 95% confidence intervals will be used.

Normality assumptions will be checked using normal probability plot for residuals. The use of transformation for a particular variable will be decided after examining the assumptions with the original scale of measurement. Analysis may be repeated without possible outliers.

The primary variable will be analyzed using an analysis of variance model for repeated measurements. Treatment differences with 95% confidence intervals will be calculated from the model. If the assumptions for the parametric models are not met suitable non-parametric models will be used.

Clinical Investigation Plan

Bioabsorbable Intramedullary Nail Fixation of Forearm Fractures in Children

Adverse Events

The safety variables to be evaluated include adverse events (AE), findings from physical and radiographic examinations, subjective reports of pain and functional outcome assessments. Further, all drop-outs will be reported. The adverse event data will include the following displays:

- AEs categorized by body system
- AEs categorized by severity grades 1-4 (mild, moderate, severe, life-threatening)
- AEs involving the region under study (RUS) specifically:
 - Fracture delayed union, nonunion and malunion
 - Hardware failure
 - Infection

All Serious Adverse Events (SAE) will be reported within 24 hours to the Sponsor. The SAEs include death, life-threatening event, medically important event, device malfunction, hospitalization, accidental exposure, persistent disability or incapacity, and cancer. In emergency SAE cases, the patients are requested to seek help in the Emergency room of the University Central Hospital. Any adverse events and their effects are reported using Case Report Form (CRF).

Quality Management

Monitoring Arrangements

The sponsor is responsible for the monitoring of this study. The principal investigator will provide sponsor with the data recorded during the study without personal identification data to allow the sponsor to check the compliance of the study with the CIP. The sponsor will appoint a monitor for assessing the investigator's compliance with the Clinical Investigation Plan and for performing source-data verification. A monitoring plan and report will be prepared.

Data Management

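### Section 10.1: 13 per group gives 80% power at 7.0 degrees for pronation but 62% for supination, and neither the SD used nor the role of 7.0 is stated

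*Protocol*

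**What the plan says.** Protocol section 10.1 (Sample Size Considerations) contains these elements, in this order:

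- The outcome: "Primary outcome variable in this study is loss of supination and pronation". No hierarchy between the two movements and no combined score is defined there.
- The power, under a mislabelled heading: "The non-inferiority margin is set to be 80 % in the calculations (=Power").
- The variability: "The standard deviation (SD) is 6.1 degrees in pronation and 7.6 degrees in supination". These values accompany published reference values for motion in the age group.
- A limit in degrees: rotation with the new nail should be "not more than 15 degrees lower, compared to the rotational range of motion in TEN group".
- The inputs: "Difference between means in the groups is set as 7.0 and the Alpha as 0.05".
- The result: "The sample size is estimated to be 13 experimental subjects and 13 controls according to an unpaired two sample Student t test".
- A closing claim that this number is enough to "recognize decrease in the ROM that is clinically significant (>15 degrees of decrease in supination or pronation").

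Section 10.3 (Statistical Methods) adds "All tests will be two-sided" and calls for 95% confidence intervals. Section 8.1 treats a difference under 10 degrees as not clinically significant.

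**The concern.** One sample size and one power figure are given for an outcome with two movements and two SDs. A larger SD at the same difference needs more patients, so one 80% statement cannot be exact for both movements.

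The role of 7.0 is also open. It could be a difference to detect, a deficit to rule out, or the deficit expected with the new nail when judged against the 15-degree limit. These are different calculations with different answers. A reader who takes 80% as the power for the primary outcome would be misled about supination, and could not tell what size of supination deficit the trial is built to exclude.

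**Working it through.** **Inputs.** SD 6.1 (pronation) and 7.6 (supination), difference 7.0, alpha 0.05, power 80%, unpaired t test and 13 per group, all from 10.1; two-sided tests and 95% intervals from 10.3; limits of 15 degrees (10.1) and 10 degrees (8.1).

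**Formula.** With n per group, the standard error is SD × √(2/n), the noncentrality is λ = d / SE, and the degrees of freedom are 2n − 2. Power is the probability that a noncentral t with noncentrality λ exceeds the critical value, which is 2.064 for 24 degrees of freedom (two-sided 0.05 or one-sided 0.025). For non-inferiority, d is the margin minus the true deficit.

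**Reproducing the plan's figure.** Pronation: SE = 6.1 × √(2/13) = 2.393; λ = 7.0 / 2.393 = 2.926; power 80.1%. The required n is 12.96, so 13. The stated number is reproduced.

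**Reading 1: 7.0 is the difference to detect.** Supination: SE = 7.6 × √(2/13) = 2.981; λ = 7.0 / 2.981 = 2.348; power 61.5%. The required n is 19.5, so 20 per group. A margin of 7.0 with true difference 0 and one-sided 0.025 gives the same two figures.

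**Reading 2: 7.0 is the expected deficit against 15 degrees.** Here d = 15 − 7 = 8.
- Pronation: λ = 8 / 2.393 = 3.344; power 89.4%.
- Supination: λ = 8 / 2.981 = 2.684; power 73.1%. The required n is 15.2, so 16 per group.

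**An averaged SD.** (6.1 + 7.6) / 2 = 6.85. In reading 2 this gives power 81.5% and a required n of 12.55, so again 13. Two different derivations therefore reach the printed number, and the text identifies neither.

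**Power and limits by movement** (13 per group unless stated)

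| Quantity | Pronation | Supination |
|---|---|---|
| Reading 1 | 80% | 62% |
| Reading 1, all 35 analysed (18/17) | – | 75% |
| Reading 2 | 89% | 73% |
| Reading 2, all 35 analysed (18/17) | – | 86% |
| Difference detectable with 80% power | 7.0 degrees | 8.7 degrees |
| Margin 15, true difference 0 | >99.9% | 99.8% |
| Margin 10, true difference 0 | 98% | 90% |
| Largest true deficit with 80% power, margin 15 | 8.0 degrees | 6.3 degrees |
| Largest true deficit with 80% power, margin 10 | 3.0 degrees | 1.3 degrees |

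The last two rows are the margin minus the detectable difference, for example 15 − 8.7 = 6.3.

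**Tolerance to the SD.** With true difference 0, 80% power needs a margin of 6.99 / 6.1 = 1.145 SDs. It therefore holds up to an SD of 15 / 1.145 = 13.1 degrees at a 15-degree margin, or 10 / 1.145 = 8.7 degrees at a 10-degree margin.

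**The case against.** The strongest reply has four parts.

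1. *The primary variable may be one combined rotation.* Section 10.1 uses the singular, its limit refers to rotational motion, and the Price classification grades loss of forearm rotation. But 10.1 also gives separate SDs and speaks of supination or pronation in its closing claim. A combined reading does not rescue the number either. If the movements are independent, the SD of their sum is √(6.1² + 7.6²) = 9.75, and power for 7.0 degrees is about 42%. For the sum to have an SD as small as 6.1, the correlation would have to be (37.21 − 94.97) / 92.72 = −0.62.
2. *The sidedness of alpha is not given in 10.1.* In reading 2 with one-sided 0.05, supination power would be 83.2%. That is correct arithmetic, but it conflicts with the two-sided tests and 95% intervals in 10.3 and with the 95% interval rule in 10.2.
3. *The precision is limited.* This stands. The SDs describe normal motion rather than loss after fracture, and the planned analysis is a repeated-measures model rather than a t test. The figures here check the calculation in 10.1; they do not predict the power of the final analysis.
4. *The consequence is small.* This largely stands. The number for pronation is right in reading 1, and the closing 15-degree claim holds on the protocol's SDs.

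**Conclusion.** The point holds. The single 80% figure is correct for pronation at a 7.0-degree difference and is not delivered for supination: 62% if 7.0 is the difference to detect or rule out, 73% if it is the expected deficit against 15 degrees. The corresponding needs are 20 and 16 per group, against 13. That pronation's SD was the one used is an inference from the fact that it returns exactly 13.

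The conclusion rests on the protocol's SDs, the unpaired t test it names, two-sided 0.05 or its one-sided 0.025 equivalent, and each movement taken separately. No rule is stated on whether both movements must succeed, so no joint power is claimed. The trial is not shown to be too small. It is the power statement that needs correcting.

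**What to change.** Keep 35 enrolled and 13 per group. In 10.1, state which SD was used and what 7.0 stands for, then give power for each movement. Use whichever of these sentences matches the intent:

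- *Difference to detect:* With 13 evaluable subjects per group, an unpaired t test and two-sided alpha 0.05, power for a 7.0-degree difference is 80% for pronation (SD 6.1) and 62% for supination (SD 7.6).
- *Expected deficit:* With a true difference of 7.0 degrees and a 15-degree margin (two-sided 95% CI), power is 89% for pronation and 73% for supination.

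Add the non-inferiority power for each movement against whichever margin in degrees 10.2 adopts, with the assumed true difference. For true difference 0 this is >99.9% and 99.8% at 15 degrees, or 98% and 90% at 10 degrees. Close with the caveat that the SDs are of normal motion and that, with true difference 0, 80% power holds up to an SD of 13.1 degrees (15-degree margin) or 8.7 degrees (10-degree margin). If a combined rotation was meant, say so and give its SD and power instead.

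The cost is one rewritten paragraph, with no extra patients and no change to the primary variable or design. The sponsor has to disclose that supination power at the stated 7.0 degrees is 62% or 73%, not 80%.

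### Section 10.1 applies its 15-degree limit to total forearm rotation in one sentence and to supination or pronation singly in another, and the primary variable is never defined as a sum or as two endpoints

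*Protocol*

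**What the plan says.** Section 10.1 (Sample Size Considerations) names loss of supination and pronation as the primary outcome. It requires that the new nail "result to the forearm rotational range of motion that is not more than 15 degrees lower" than in the titanium group, and takes the 15 degrees from Price's classification. It gives SDs by movement only: 6.1 degrees for pronation and 7.6 for supination. With a difference of 7.0, alpha 0.05 and an unpaired t test it arrives at 13 per arm. It then adds that this number is enough to recognise a clinically significant decrease, described as ">15 degrees of decrease in supination or pronation in ActivaNail compared to TEN group".

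Section 1.1.11 lists "Loss of supination and pronation of the forearm (graded according to the table below"). That table (Table 1, Price) puts in its top grade a loss of up to 15 degrees, with the entry "loss of forearm rotation and no complaints with strenuous activity". The next grade is "A loss of forearm rotation of 15° to 30° and only mild complaints with strenuous physical activity".

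Two other places state limits. Section 8.1 (Primary Objectives) says: "The potential difference less than 10 degrees are to be determined not clinically significant", without naming the movement. Section 10.2 (Statistical Hypothesis) declares non-inferiority when the upper 95% confidence limit for the difference is at most 5 %, which is not in degrees.

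**The concern.** The same 15 degrees is attached to two different quantities. Supination and pronation together make up forearm rotation, so a limit on each movement allows a larger combined deficit than the same limit on rotation. The primary variable does not settle the matter, because it names both movements without saying whether they are added or judged separately. The sample size cannot settle it either, since it rests on a single-movement SD.

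There is a second mismatch. Table 1 grades one child's loss together with that child's symptoms, and section 1.1.9 compares the injured forearm with the healthy one. Section 10.1 reuses the table's cut-off as a difference between groups.

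At stake is the trial's main claim of comparable motion. If the variable stays open, the same data can support opposite conclusions, and the choice could be made after the data are seen.

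**Working it through.** **Inputs from 10.1 and Statistical Methods (10.3).** SD 6.1 (pronation) and 7.6 (supination), difference 7.0, alpha 0.05, two-sided tests, power 80%, 13 per arm. The correlation r between the two movements is not given. It is an assumption here, shown at 0 and +0.5, with other values where noted.

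**1. The plan's own figure.** Exact two-sided unpaired t test, effect size 7.0/SD:
- SD 6.1: n = 12.96, so 13 per arm; power at 13 is 80.1%. This matches the plan.
- SD 7.6: n = 19.5, so 20 per arm; power at 13 is 61.5%.

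Of the two stated SDs, only the pronation SD gives 13 under the stated two-sided 5% and 80%.

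**2. The same test on total rotation.** SD of the sum = √(6.1² + 7.6² + 2·r·6.1·7.6) = √(37.21 + 57.76 + 92.72·r).

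| r (assumed) | SD of sum | Power for 7 degrees, 13 per arm | n per arm for 80% |
|---|---|---|---|
| −0.5 | 7.0 | 69% | 17 |
| 0 | 9.7 | 42% | 32 |
| +0.5 | 11.9 | 30% | 47 |
| +1 | 13.7 | 24% | 62 |

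**3. Do the two readings of the 15 degrees lead to different conclusions?** Simulation with 13 per arm, normal data and the SDs above. The rule is that the upper limit of the two-sided 95% confidence interval for the deficit lies below 15 degrees, either for both movements or for their sum. Ranges run over r = 0 to +0.5.

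| True deficit per movement | Total deficit | Passes, per movement | Passes, total rotation |
|---|---|---|---|
| 7.5 | 15 | 58 to 62% | about 2.5% |
| 10 | 20 | 19 to 26% | about 0.1% |
| 14.9 | 29.8 | 0.1 to 0.5% | 0% |

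The 2.5% in the first row is what a 95% confidence rule should give at its own limit. The per-movement rule passes more than half of such trials.

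**4. How large a combined deficit could pass?** The 95% half-width is 2.064·SD·√(2/13): 4.9 degrees for SD 6.1 and 6.2 for SD 7.6. The largest observed deficits that meet a 15-degree limit are therefore about 15 − 4.9 = 10.1 and 15 − 6.2 = 8.8, together about 19 degrees.

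**5. Individual grade against group difference.** If the titanium group's mean loss is c, a test group 15 degrees worse has mean loss c + 15, which exceeds 15 for any c above 0. With c = 5 (assumption) it is 20. The margin alone therefore does not place the test group in the top grade.

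**The case against.** The sentence with the per-movement limit is a remark on what the sample can detect, not a success rule. The formal rule is in 10.2, and 8.1 treats only differences below 10 degrees as unimportant. The two sentences in 10.1 can also be true together: a loss above 15 degrees in one movement, with the other unchanged, is also a loss above 15 degrees of rotation. Price grading and reporting of the raw measurements are already planned. The cited source is not at hand, and because section 1.1.9 gives the average range as 90/90, the 90-degree upper band in Table 1 does not prove that the table means a sum.

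Most of this stands as a limit on the point. A reader might infer that a device costing almost 30 degrees of rotation could be passed as not clinically significant. The protocol does not support that. It never says that 15 degrees or less in each movement is unimportant, deficits of 14 + 14 exceed the 10 degrees of 8.1 in each movement, and a confidence-limit rule would almost never pass such a loss (working, steps 3 and 4). About 30 degrees is only a theoretical bound.

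The objection does not remove the ambiguity. The 5 % in 10.2 cannot be converted to degrees from the document, 8.1 does not name its movement, and 15 degrees is the only tolerated deficit against the titanium group that 10.1 states for rotational motion.

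**Conclusion.** The point holds as an undefined primary variable with one limit placed on two quantities. It matters most at true combined deficits of roughly 15 to 20 degrees, where the per-movement reading passes 19 to 62% of trials and the total-rotation reading at most about 2.5%. The stated 80% power belongs to pronation alone. For total rotation, the quantity named in the margin sentence, power for a 7-degree difference is about 42% at correlation 0 and 30% at +0.5.

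These figures assume normal data, the SDs in 10.1 applied to loss of motion, an assumed correlation, and a confidence rule of 15 degrees, which 10.2 itself does not state. The documents do not settle which limit is clinically right, and this point does not claim to.

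A reader might also infer that 13 per arm is too few under any reading. That does not follow. For a 15-degree margin on total rotation with no true difference, the normal approximation Φ(15/(SD·√(2/13)) − 1.96) gives 97.5% power at r = 0 and 89.6% at r = +0.5.

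**What to change.** - In 1.1.11 and 10.1, define the primary variable once. Total rotation (supination plus pronation), as loss against the healthy forearm, is the quantity that Table 1 and the margin sentence name.
- State one limit in degrees on that variable. Reconcile with it the sentence on supination or pronation in 10.1, the 10-degree statement in 8.1 and the 5 % rule in 10.2.
- Restate the power that 13 per arm gives for that variable, with an SD for it and its source, or with a range of correlations if none is available.
- Report each movement separately, and the number of children per arm whose own loss is at most 15 degrees, beside the mean difference. Do not present the group margin as showing an excellent outcome.

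The cost is protocol wording and a recalculation. Both angles are already measured, so no new data are needed. The limit becomes stricter than the per-movement reading, and the stated power for a 7-degree difference falls.
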